7.3.1 Primary endpoint analyses

The achievement of ppPASI50 at Week 16 is the primary endpoint in this trial and represents a binary variable with values of 0 (= non-response) or 1 (=response). Prior to treatment unblinding for the optional week 16 interim analysis, it may be decided to use the ppPASI75 as the primary endpoint (instead of ppPASI50 which will then be considered as a secondary endpoint); if applicable, such decision will be documented in the Trial Statistical Analysis Plan (TSAP).

The primary analysis of the unadjusted absolute risk difference versus Placebo will be calculated simply as the difference in the observed proportion of patients with ppPASI50 at week 16 for each treatment scenario, for the FAS. A 95% Wilson confidence interval around this difference will also be provided. In addition, a parametric bootstrap 95% confidence interval will be generated by sampling from the binomial distribution on each treatment with

number of patients and observed proportion of responders per treatment representing the sampling parameters. A hierarchical approach to the testing of both scenarios for BI 655130 versus Placebo will, however, be performed for the primary analysis in order to control for multiplicity arising as a result of the multiple treatment comparisons.

Further details will be provided in the TSAP.

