
based on the observed proportion of patients with ppPASI50 at week 16 for BI 655130 and placebo will be assessed descriptively, for the Full Analysis Set (FAS), and 95% Wilson confidence intervals (CIs) will also be provided. The FAS comprises all participants who were randomised, received at least one dose during the trial, and had a baseline measurement for the primary endpoint. The influence of the stratification variable on the primary endpoint will be characterized in exploratory analyses.
 
Safety data will be presented using descriptive methods.
			

FLOW CHART

Trial Periods	Screening ¹	Randomised Treatment Period										Post treatment follow-up	
		2 ²	3	4	5	6	7	8	9	10	11 PE ³	12	13 EOT ⁴
Visit	1												
Week	-4 to -1				2	4	6	8	10	12	16	24	32
Day	-28 to -7	1	4±2	8±3	15±3	29±3	43±3	57±3	71±3	85±3	113±3	169±7	225±7
Informed Consent	X												
Inclusion/exclusion criteria	X	X											
Demographics, Medical History	X												
Physical Examination	X ^{12,C}	X ^T	X ^T	X ^T	X ^T	X ^T	X ^T	X ^T	X ^T	X ^T	X ^C	X ^T	X ^{12,C}
Vital Signs	X	X	X	X	X	X	X	X	X	X	X	X	X
Pregnancy testing ⁵	X ^s	X ^{u,(s)}				X ^{u,(s)}		X ^{u,(s)}		X ^{u,(s)}	X ^{u,(s)}	X ^{u,(s)}	X ^{u,(s)}
Safety Laboratory tests	X	X	X	X	X	X	X	X	X	X	X	X	X

Proprietary confidential information © 2018 Boehringer Ingelheim International GmbH or one or more of its affiliated companies

Trial Periods	Screen- ing ¹	Randomised Treatment Period										Post treatment follow-up		
		1	2 ²	3	4	5	6	7	8	9	10	11 PE ³	12	13 EOT ⁴
Week	-4 to -1					2	4	6	8	10	12	16	24	32
Day	-28 to-7	1	4±2	8±3	15±3	29±3	43±3	57±3	71±3	85±3	113±3	169± 7	225±7	
Assign/Administer study drug		X					X		X		X			

Palmoplantar Pustular Psoriasis Area and Severity Index (ppPASI)	X	X	X	X	X	X	X	X	X	X	X	X	X	X
PPP Physician Global Assessment (pppPGA)	X	X	X	X	X	X	X	X	X	X	X	X	X	X

12-lead ECG	X	X				X		X		X	X	X	X	X
Local Tolerability		X				X		X		X				
Adverse events	X	X	X	X	X	X	X	X	X	X	X	X	X	X
Concomitant Therapy	X	X	X	X	X	X	X	X	X	X	X	X	X	X
Completion of participation ⁴														X

Footnotes:

¹ The time window for Visit 1 may be extended at the discretion of the Local Clinical Monitor (CML) in conjunction with the TCM (Trial Clinical Monitor) on a case by case basis.

² Day of Randomisation / Day of first administration of randomised medication.

³ PE – Primary Endpoint Visit.

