2.0 RATIONALE, OBJECTIVES, AND BENEFIT - RISK ASSESSMENT

2.1 RATIONALE FOR PERFORMING THE TRIAL

BI 655130 is in development for the treatment of Palmoplantar Pustulosis. The first trial to be conducted in PPP patients is a proof-of-concept, phase IIa trial. The rationale to perform this trial is based on the published human genetic linkage between the target disease PPP and the IL36 pathway targeted by BI 655130 [[R16-0950](#); [R16-3561](#)], the functional linkage between the IL36 pathway and PPP [[R16-3543](#)] and the high unmet medical need in PPP.

There is currently no drug specifically approved for the treatment of PPP and it is notoriously difficult to treat. Patients usually end up being treated with the currently available systemic treatment options including retinoids, PUVA, methotrexate, ciclosporine and topical corticosteroids. Unfortunately, the current treatment options are not effective in reducing duration and severity of PPP. Thus, there is high unmet medical need for PPP.

The results from this trial will enable the design of the further developmental program and in case that positive efficacy signals can be confirmed the results will form the basis for discussions with regulatory agencies.

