7.2 NULL AND ALTERNATIVE HYPOTHESES

There will be no formal hypothesis testing performed in this trial. As an exploratory Phase II trial in patients with palmoplantar pustulosis, inferences concerning the efficacy of BI 655130 will be based on the magnitude of the observed difference(s) versus Placebo on the proportion of patients who achieve a 50% reduction from baseline in the ppPASI score (ppPASI50) at Week 16, as well as on other efficacy endpoints, such as the % change in ppPASI from baseline, ppPASI75, etc.

The study has 3 treatment arms (BI 655130 900 mg, BI 655130 300 mg and placebo), and there are 2 scenarios of interest, as described below:

- (1) Scenario 1: Examines the maximum effect of (BI 655130 900 mg or 300 mg) versus Placebo
- (2) Scenario 2: Examines the effect of BI 655130 300 mg versus Placebo

A sample size justification regarding the scenarios of interest and potential decision boundaries for comparison can be found in [Section 7.7](#).

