7.7 DETERMINATION OF SAMPLE SIZE

The study is intended to show an increase for BI 655130 over placebo in terms of the proportion of patients achieving a ppPASI50 response at Week 16. There is currently no clinical trial data available in the published literature that describes a placebo response on the ppPASI50 in the population of patients with palmoplantar pustulosis. The success probability for the primary endpoint on this PoCC trial has, therefore, been derived under the assumption that the difference between BI 655130 and Placebo is 0.30 and that a total N of 60 patients (fixed according to feasibility considerations) will be studied in a 1:1:1 ratio (i.e. 20 patients per treatment group).

Simulations in SAS[®] were used to derive estimates of the probability that a single trial would demonstrate an observed difference in proportions between BI 655130 and Placebo that was equal or greater than a defined threshold under a positive scenario whereby the expected difference in proportions is 0.3 in favour of BI 655130. For identifying such a target threshold, a minimum probability of 0.80 was defined. For each trial simulation, the response for each patient on each treatment was generated using a binomial distribution utilizing the expected treatment response rates as noted in [Table 7.7:1](#) below. The trial observed proportions for each treatment were calculated and then the treatment comparisons, according to scenario 1 and scenario 2, were each compared against a range of threshold values using a hierarchical approach. A total of 100,000 trial simulations were performed. In addition, the probability of a false positive declaration being made given the specified target threshold(s), so-called negative scenario, was also determined.

Table 7.7:1 Probability to Achieve the Threshold Difference in Treatments given Expected Treatment Response Rates on ppPASI50 and a Total Sample Size of 60 Patients

Population Response Rate			Expected Response Difference (BI vs PLC)	Threshold (Observed Difference)	Probability Threshold Exceeded ¹	False Positive Rate (%) ²
Low Dose BI	High Dose BI	Placebo				
SCENARIO 1 (maximum of [BI 655130 900 mg or 300 mg] vs. Placebo)						
0.45	0.45	0.15	0.3	0.20	93%	11%
0.50	0.50	0.20	0.3	0.20	92%	15%
0.55	0.55	0.25	0.3	0.20	91%	18%
0.60	0.60	0.30	0.3	0.20	91%	20%
SCENARIO 2 (BI 655130 300 mg vs. Placebo)						
0.45	0.45	0.15	0.3	0.15	87%	7%
0.50	0.50	0.20	0.3	0.15	86%	10%
0.55	0.55	0.25	0.3	0.15	85%	12%

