0.60	0.60	0.30	0.3	0.15	85%	14%

Hierarchical testing: scenario 2 only tested if outcome on scenario 1 \geq specified threshold.

¹ Positive scenario: Assuming the expected response rate difference, the probability that the BI 655130 response rate exceeds that of Placebo by at least the threshold amount is displayed.

² Negative scenario: The probability that the BI 655130 response rate exceeds that of Placebo by at least the threshold amount assuming that treatments are equal.

In summary, for a total N of 60 patients, a 1:1:1 allocation ratio to BI 655130 900 mg, BI 655130 300 mg, and Placebo, then under the assumption of a target difference between each dose of BI 655130 and Placebo of 0.30 [positive scenario] for the proportion of responders on the primary endpoint at week 16, this trial will be able to show:

- An observed difference in response rates of at least 0.20, for the maximum of (BI 655130 900 mg and BI 655130 300 mg) versus Placebo, with 91% probability (assuming a Placebo response rate from 0.15 through 0.30). The false positive decision probability in this case ranges from approx. 11%-20% under the assumption of no treatment difference;
- An observed difference in response rates of at least 0.15, for BI 655130 300 mg versus Placebo, with 85% probability (assuming a Placebo response rate from 0.15 through 0.30). The false positive decision probability in this case ranges from approx. 7%-14% under the assumption of no treatment difference.

The hierarchical nature of the comparisons, with rejection of the maximum of (BI 655130 900 mg or BI 655130 300 mg) versus Placebo (scenario 1) required prior to proceeding to the test of BI 655130 300 mg versus Placebo (scenario 2), warrants that the overall success probability is at least 85% while the overall false positive rate [under negative scenario] is controlled at 20% (one-sided).

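### One of the two primary effect estimates is the better-observed dose arm minus placebo, which overstates the effect by 4 to 6 points on average if the doses are equal, and no 900 mg contrast is named

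*Protocol*

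**What the plan says.** Section 7.2 rules out formal testing and states that "inferences concerning the efficacy of BI 655130 will be based on the magnitude of the observed difference(s) versus Placebo". It then lists two scenarios of interest. Scenario 1 "Examines the maximum effect of (BI 655130 900 mg or 300 mg) versus Placebo". Scenario 2 is 300 mg versus placebo. There is no scenario for 900 mg alone.

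Section 7.3.1 carries this into the primary analysis. The risk difference is "calculated simply as the difference in the observed proportion of patients with ppPASI50 at week 16 for each treatment scenario, for the FAS", and "A 95% Wilson confidence interval around this difference will also be provided". A parametric bootstrap interval is added, and further details are left to the trial statistical analysis plan (TSAP).

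The synopsis describes the primary risk difference only in general terms, as "based on the observed proportion of patients with ppPASI50 at week 16 for BI 655130 and placebo will be assessed descriptively", without separating the doses. The primary objective in Section 2.2 compares either dose with placebo. Section 7.7 plans the trial "under the assumption of a target difference between each dose of BI 655130 and Placebo of 0.30", so both doses have the same assumed effect.

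**The concern.** Read as written, the maximum is more than a decision statistic. It is one of the two quantities reported as the primary treatment effect, with an ordinary interval around it. Taking the larger of two observed rates favours whichever arm happened to do well by chance, so its expected value lies above the true effect when the doses are similar.

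The second problem is attribution. If 300 mg has the higher observed rate, Scenario 1 and Scenario 2 give the same 300 mg number. The reader learns that 900 mg did no better, but no primary estimate for 900 mg has been named.

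Section 2.1 says that "The results from this trial will enable the design of the further developmental program", and Section 7.2 rests inference on the size of the observed difference. The protocol does not say which estimate will feed later planning. What is at stake is therefore the reported effect size and the dose it belongs to, not the go/no-go decision.

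**Working it through.** **Inputs (Section 7.7).** 20 patients per arm; placebo rate 0.15, 0.20, 0.25 or 0.30; true difference 0.30 for both doses (positive case) or 0 (negative case); Scenario 1 threshold 0.20, that is, at least 4 of 20 responders more than placebo.

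**Method.** Exact enumeration of all 21 × 21 × 21 outcomes of three independent Binomial(20, p) arms.

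**Step 1: confirm what Scenario 1 is.** The table gives P(max(900 mg, 300 mg) − placebo ≥ 0.20), with the protocol's Table 7.7:1 value in brackets.

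| Placebo rate | True difference 0.30 | True difference 0 |
|---|---|---|
| 0.15 | 93.6% (93%) | 10.8% (11%) |
| 0.20 | 92.7% (92%) | 14.5% (15%) |
| 0.25 | 91.9% (91%) | 17.2% (18%) |
| 0.30 | 91.4% (91%) | 19.1% (20%) |

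Agreement is within about 1 point. A single fixed dose arm would give 80–82% and 6–11%, so Scenario 1 is the larger of the two observed rates.

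**Step 2: bias with equal doses.** For two independent arms with the same true rate p,

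E[max] = p + ½·E|difference between the arms|, so bias = ½·E|difference|.

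By symmetry this equals P(300 mg strictly higher) × (mean gap when 300 mg is strictly higher).

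- True difference 0, placebo 0.15: 0.411 × 0.1075 = 0.044.
- True difference 0.30, placebo 0.15 (both doses 0.45): 0.437 × 0.1427 = 0.062. The normal approximation agrees: the one-arm standard error is √(0.45 × 0.55 / 20) = 0.111, and 0.111/√π = 0.063.

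| Placebo rate | Bias, true difference 0 | Bias, true difference 0.30 |
|---|---|---|
| 0.15 | +4.4 points | +6.2 points |
| 0.20 | +5.0 | +6.3 |
| 0.25 | +5.4 | +6.2 |
| 0.30 | +5.7 | +6.1 |

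The standard error of a fixed-arm difference, √[p(1−p)/20 + p₀(1−p₀)/20] with p₀ the placebo rate, is 0.113 to 0.150. The bias is 0.39 to 0.46 of it.

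**Step 3: the interval.** I took the Wilson interval for a difference to be the usual Newcombe form. Its lower limit lies above the true difference in 3.1–4.8% of trials when applied to the maximum, against 1.7–2.7% for a fixed arm. Two-sided coverage is 94.8–96.3% against 94.7–96.5%. Coverage holds because misses at the upper limit become rare: at placebo 0.15 and no effect, 100 − 96.3 − 3.3 = 0.4%. Root mean squared error is 0.117–0.149 against 0.113–0.150.

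**Step 4: unequal doses.** Let 900 mg have a true difference of 0.30 and 300 mg a smaller one.

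| True gap between doses | Bias against the 900 mg effect | P(300 mg strictly higher) |
|---|---|---|
| 5 points | 4.0–4.1 points | about 32% |
| 10 points | 2.4–2.5 | 21% |
| 20 points | 0.6–0.7 | 6–7% |

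**Step 5: how often 900 mg has no primary estimate.** With equal doses 300 mg is strictly higher in 41–44% of trials. In those trials the 900 mg difference lies on average 10.8–14.3 points below the reported maximum, and at least 20 points below it in 14–31% of them. This is the gap between the two arms, not the bias of the maximum.

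**The case against.** The strongest reply is that this is a decision device in an exploratory trial, and that little is lost. Section 7.2 links the scenarios to decision boundaries, Section 7.7 calibrates the thresholds on them, and no formal testing is planned. Each arm's observed response rate is needed for the bootstrap, so 900 mg minus placebo is one subtraction away. Section 7.2 speaks of differences versus placebo in a form that allows the plural, and Section 7.3.2 gives the secondary risk differences without any maximum. Whenever 900 mg does at least as well as 300 mg, the two scenarios are the two dose contrasts; with equal doses that happens in 56–59% of trials. The TSAP, which was not available for this review, may add a per-dose table. The bias is under half a standard error, and it needs doses of similar effect. About half of the 10.8–14.3 point gap is chance error downward in the 900 mg arm.

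Most of this is correct, and it limits the size of the point. Decisions, two-sided coverage and mean squared error are essentially unaffected. Equal doses are a simulation input, not a forecast of dose response. Nothing in the protocol forbids a 900 mg contrast.

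It does not remove the point. Section 7.3.1 states that the primary difference and its interval are computed per scenario, and Section 7.2 names the scenarios. This is a stated estimator, not a detail left open, and a TSAP would have to depart from that wording to repair it. Calibrating a threshold on the maximum does not correct the maximum as an estimate. The absence of testing makes the estimate more important, because inference is to rest on its magnitude.

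**Conclusion.** The concern holds. As written, one of the two primary effect estimates is the better-observed arm minus placebo, and 900 mg versus placebo is not named as a primary contrast in Section 7.2, Section 7.3.1 or the synopsis. With equal doses, the estimate is on average 4.4 to 5.7 points too high if there is no effect and 6.1 to 6.3 points too high under the planned effect. The interval's errors shift towards overstating efficacy.

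These figures rest on 20 patients per arm, placebo rates of 0.15 to 0.30 and independent binomial responses. The interval results also assume the Newcombe form. The bias fades as the doses separate and is below 1 point at a 20-point gap. The 0.20 threshold and the false positive rates in Table 7.7:1 already allow for taking the maximum and stand. The point should be fixed because it affects the trial's reported effect size and its attribution to a dose. It does not threaten the trial's decision rule.

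**What to change.** In Sections 7.2 and 7.3.1, name two primary estimates: 900 mg minus placebo and 300 mg minus placebo, each with the Wilson interval already planned, and both reported whatever the outcome. State that the maximum serves only for comparison with the 0.20 threshold and is not an effect estimate. The thresholds and the hierarchical order stay as they are. Carry the same wording into the TSAP.

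The cost is a change of text; no new data or further simulation is needed. The sponsor gives up a more favourable headline figure: about 4 to 6 points on average if the doses are similar, possibly more in a single trial, and almost nothing if 900 mg is 20 points better. A reader can still pick the larger of the two differences, so selection is not prevented. Both figures are then visible, however, and each belongs to a fixed dose.

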7.3.2 Secondary endpoint analyses

For the secondary binary endpoints, for the FAS, the unadjusted absolute risk difference versus Placebo will be calculated and a 95% Wilson confidence interval around this difference will also be provided. In addition, a parametric bootstrap 95% confidence interval will also be generated.

For secondary continuous endpoints, mean changes from baseline will be analysed using a restricted maximum likelihood (REML)-based repeated measures approach (see [Section 7.3](#)).

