5.1.2 Secondary Endpoint(s)

- Treatment success defined as achieving a clinical response of 0 or 1=clear/almost clear via PPP Physicians Global Assessment (pppPGA) at week 16
- ppPASI75 at week 16
- Percent change from baseline in the ppPASI at week 16

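### The supplementary parametric bootstrap 95% interval gives an arm with 0/20 (or 20/20) responders no variance, so it understates uncertainty for rare binary endpoints

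*Protocol*

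**What the plan says.** Protocol section 7.3.1 plans two 95% intervals for the week 16 risk difference: a Wilson interval and, in addition, a parametric bootstrap interval. The bootstrap samples from a binomial distribution in each arm, with "number of patients and observed proportion of responders per treatment representing the sampling parameters".

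Section 7.3.2 carries both to the secondary binary endpoints. The Wilson interval comes first ("a 95% Wilson confidence interval around this difference will also be provided"), and then "a parametric bootstrap 95% confidence interval will also be generated". The sampling scheme is not restated there, so I take it to be that of 7.3.1. Neither section has a rule for an arm with no responders or all responders, and neither says which interval is interpreted if they disagree.

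The secondary binary endpoints in section 5.1.2 are "ppPASI75 at week 16" and treatment success, defined as "achieving a clinical response of 0 or 1=clear/almost clear via PPP Physicians Global Assessment (pppPGA) at week 16". Section 7.7 fixes 20 patients per arm. Section 7.3.1 also provides that, before unblinding for the optional interim analysis, "it may be decided to use the ppPASI75 as the primary endpoint".

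**The concern.** A parametric bootstrap takes its whole variance from the fitted model. If the fitted response rate is exactly 0, every resample returns 0, and the arm is treated as if its true rate were known to be 0. Twenty patients without a response do not justify that.

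This bears on the secondary endpoints. ppPASI75 cannot be more frequent than ppPASI50, whose assumed placebo rate in Table 7.7:1 starts at 0.15. Section 3.3.2 requires at least moderate pppPGA at baseline, so clear or almost clear needs a fall of two grades or more. Under section 7.5 most missing values, and all values after rescue, count as failures. A placebo count of 0/20 is therefore plausible.

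At stake is whether a reported 95% interval conveys the uncertainty it claims. Section 7.2 plans no formal testing and names ppPASI75 among the endpoints that inform inference, so the intervals are the main statement of precision.

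**Working it through.** **Inputs.** n = 20 per arm (7.7) and binomial resampling at the observed proportions (7.3.1). The protocol states no ppPASI75 or pppPGA 0/1 rates, so the rates below are assumptions. I read the Wilson interval for a difference as Newcombe's, built from the Wilson limits of each arm. I read the bootstrap as the percentile type and computed it exactly, as if with unlimited resamples.

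**The plan's own figures.** The protocol states no operating figure for the bootstrap interval. As a check on the set-up, exact enumeration of Table 7.7:1 (placebo 0.15/0.20/0.25/0.30) gives:
- scenario 1: 93.6/92.7/92.0/91.4%, false positives 10.8/14.5/17.2/19.1%;
- scenario 2: 87.7/86.4/85.6/85.1%, false positives 6.8/9.5/11.5/13.0%.

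All are within about 1 point of the table.

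**Chance of an empty arm.** P(0/20) = (1 - p)^20, which is 67% at p = 0.02, 36% at 0.05, 12% at 0.10 and 4% at 0.15.

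**Intervals for given results.**
- *Bootstrap.* With placebo at 0/20 the resampled difference is Binomial(20, x/20)/20. It cannot be negative, so the lower limit cannot fall below 0. For x = 1: P(0) = 0.358, P(≤2) = 0.925 and P(≤3) = 0.984, so the interval is 0/20 to 3/20. For x = 4: P(0) = 0.012, P(≤1) = 0.069, P(≤7) = 0.968 and P(≤8) = 0.990, so it is 1/20 to 8/20.
- *Newcombe.* Lower = d - √[(p1 - l1)² + (u0 - p0)²]; upper = d + √[(u1 - p1)² + (p0 - l0)²]. At 0/20 the Wilson upper limit is z²/(n + z²) = 3.84/23.84 = 0.161. For 4/20 v 0/20: lower = 0.20 - √(0.1193² + 0.1611²) = -0.0005; upper = 0.416.

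| Active v placebo | Bootstrap | Newcombe |
|---|---|---|
| 0/20 v 0/20 | 0.00 to 0.00 | -0.161 to 0.161 |
| 1/20 v 0/20 | 0.00 to 0.15 | -0.116 to 0.236 |
| 2/20 v 0/20 | 0.00 to 0.25 | -0.077 to 0.301 |
| 4/20 v 0/20 | 0.05 to 0.40 | -0.001 to 0.416 |
| 5/20 v 0/20 | 0.10 to 0.45 | 0.04 to 0.47 |

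**Coverage.** For each pair of true rates, I summed the binomial probabilities of all 21 × 21 outcomes whose interval contains the true difference.

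| True rates | Bootstrap | Newcombe |
|---|---|---|
| 10% v 2% | 84.8% | 99.1% |
| 20% v 2% | 90.8% | 97.7% |
| 22% v 6% | 92.3% | 97.0% |
| 25% v 3% | 91.9% | 97.0% |
| 30% v 7% | 92.4% | 96.4% |
| 20% v 5% | 95.8% | 96.3% |
| 45% v 15% | 95.8% | 94.7% |
| 60% v 30% | 95.3% | 94.7% |

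The last three differences are multiples of 1/20. A closed bootstrap limit can then fall exactly on the true value, which flatters coverage. With smaller differences coverage is lower still (7.3% v 2%: 76.9%). Over true differences from 0 to 0.30, mean bootstrap coverage is 86.0%, 90.5% and 92.8% for placebo rates of 0.01-0.05, 0.05-0.10 and 0.10-0.20. Newcombe gives 97.9%, 96.7% and 95.5%. A basic instead of a percentile bootstrap gives 86.8%, 92.3% and 93.2%, so the choice of type does not remove the shortfall.

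**False exclusion of zero.** With equal true rates, the bootstrap excludes zero in 0.1% of trials at 2%, 1.2% at 5%, 3.9% at 10% and 4.9% at 15% and 20%.

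**The case against.** The strongest reply is that little hangs on this interval. The Wilson interval stands first in the same section and is sound at 0/20, so a reader who meets 0.00 to 0.00 will see -0.16 to 0.16 beside it. The bootstrap is additional, the trial is exploratory, and the decision thresholds in 7.7 are set on observed differences. The low rates that produce the shortfall are assumed. All of this stands, and it makes the severity low.

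It could also be said that an empty arm is a detail for the TSAP. That does not stand: the protocol itself fixes the sampling rule, and that rule fails at 0/20.

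A reader might infer something stronger, namely that the bootstrap would produce spurious effects by excluding zero where Newcombe does not. The calculations do not support this. Among results favouring active treatment, it happens only at 4/20 v 0/20 and its mirror 20/20 v 16/20, where Newcombe's lower limit is -0.0005. At 10/20 v 4/20 and 16/20 v 10/20 the conflict runs the other way. At true rates of 20% v 2% the bootstrap excludes zero in 45% of trials against 30% for Newcombe, but a real difference of 0.18 exists there, so those exclusions are correct.

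**Conclusion.** The point holds as a defect of a planned, supplementary interval. The rule in 7.3.1, carried to 7.3.2, assigns no variance to an arm with no or all responders. The collapse to zero width at 0/20 v 0/20, and a lower limit that cannot go below 0 when placebo is 0/20, follow from the rule without any assumption about rates.

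How often it matters does rest on assumed rates. At placebo rates of about 2% to 7%, with a true difference off the 1/20 grid, coverage is about 85% to 93% for the differences of 0.08 to 0.23 tabulated. It is near nominal at some grid points and about 95% at the ppPASI50 planning rates. It would be wrong to conclude that the ppPASI50 primary analysis is compromised, or that false positives are inflated.

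Severity is low. It would matter more if ppPASI75 became the primary endpoint, since the same interval would then accompany the primary result.

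**What to change.** In 7.3.1 and 7.3.2, state that the already planned Wilson-score (Newcombe) interval for the difference is the one interpreted, and drop the parametric bootstrap interval for the binary endpoints. If it is kept, at least do not report it when an arm has 0 or all responders. That removes the collapse, although some shortfall at low rates would remain. The cost is one sentence in each section and matching text in the TSAP, best settled before any decision to make ppPASI75 primary. Patients, data collection and sample size are unaffected.
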